## 7. STUDY POPULATION

### 7.1. Subject Disposition

Each subject who provided informed consent will be accounted for in this study.

A table displaying the number and percentage of randomized subjects in each analysis set by starting dose treatment group and the two treatment groups combined will be provided for the 24-Week Analysis and the Final Analysis. For the Final analysis, this table will also include these counts and percentages on subjects who enter the Dose Maintenance Period, as there may be subjects who do not return after the Dose Titration Period, i.e., after their Week 24 visit.

A summary of subject accountability by treatment period and treatment group will also be presented. The summary will include the number of subjects screened, number of screen failures, number of subjects randomized, number subjects that were randomized but did not receive a dose of study drug and the number of subjects and percentage of randomized subjects in the Safety, Full and Per Protocol/modified Per Protocol analysis sets.

The subject disposition table for the 24-Week Analysis will display statistics for the Dose Titration Period. The subject disposition table for the Final Analysis will display statistics for the 48-Week treatment period (i.e. both the Dose Titration and the Dose Maintenance treatment periods).

These tables will display by treatment group and overall the number and percentage of randomized subjects with each of the following two statuses at the end of the specific treatment period:

- Completed the treatment period;
- Discontinued from the study.

The number and percentage of those who discontinued the study during the treatment period will be displayed by reason for non-completion.

One of the following 15 reasons for non-completion should have been recorded in the eCRF for each subject who did not complete the study:

- Discontinuation from study drug
- Subject withdrawal of consent
- Lost to follow-up
- Study drug non-compliance
- Investigator judgment

- Prohibited Therapy
- Start of chronic dialysis or kidney transplantation
- Death
- Sponsor termination of study
- Protocol violation
- Adverse event
- Pregnancy
- Administrative reasons
- Two consecutive Hgb values of < 8.0 g/dL (< 8.5 g/dL per original protocol) and patient does not qualify for ESA Rescue Therapy
- Other

A by subject listing, showing the subject disposition information, including the analysis set flags for all screened subjects, sorted by subject number within treatment group will be produced. For the Final analysis only, if there are less than 3 subjects in the 'Permitted' ESA Rescue Therapy subgroup, a separate disposition listing for only those subjects will be provided instead of a table.

#### **7.1.1. Discontinuation from Study for Use of Prohibited Therapies**

A table displaying the number and percentage of subjects in the Safety analysis set who discontinued the study with use of each of the following prohibited therapies as the primary reason will be provided:

- IV iron
- Blood transfusion
- ESA with the exception of ESA Rescue Therapy under the conditions permitted by protocol.
- Oral iron therapy other than KRX-0502 as treatment for iron deficiency except for multivitamins containing iron
- Phosphate binder other than KRX-0502
- Commercial ferric citrate
- Aluminum-containing therapies
- Investigational drug other than the KRX-0502

The statistics in this table will be shown for each of the starting dose treatment groups and the two treatment groups combined.

#### **7.1.2. Discontinuation from Study Drug**

A table will display the number and percentage of subjects in the Safety Analysis set whose primary reason for discontinuation of treatment with the study drug was as follows:

- Adverse event
- Two consecutive Hgb below 8.0 g/dL (below 8.5 g/dL per original protocol) more than 3 days apart and subject does not qualify for ESA Rescue Therapy
- Pregnancy
- Withdrawal by subject
- Other

The statistics will be displayed by starting dose treatment group and the two treatment groups combined for the Dose Titration treatment period and the Dose Maintenance treatment period.

#### **7.2. Protocol Deviations**

Protocol deviations (PDs) will be collected on a PD log.

Protocol deviations will be reviewed by the Keryx Team, and their status confirmed by the time that all data are cleaned for the 24-Week analysis and the Final Analysis.

Section 6.3.5 lists PDs that affect the validity of the efficacy measurements and result in exclusion of subjects from the PP Analysis Set.

A listing of PDs for subjects who are excluded from the PP analysis set will be generated.

#### **7.3. Demographic and Other Baseline Characteristics**

Baseline demographic and other baseline characteristics for subjects in the PP analysis and Safety analysis sets will be summarized by starting dose group and these two treatment groups combined, as well as by dosing sequence group, using descriptive statistics and by subject listings of these data will be presented by starting dose group. In addition, comparable summary tables and by subject listings will be provided for the subgroup of FAS who received ESA rescue therapy under the conditions permitted by the protocol given that there will be efficacy analyses performed for this subgroup. For the Final analysis only, if the subgroup includes less than 3 subjects, by subject listings of the data for these subjects will be provided instead of tables.

Note, no comparisons of the baseline demographic and other baseline characteristics between treatment groups are carried out for this study.

The demographic characteristics include:

- Age (years)
- Age Category
- Sex
- Ethnicity
- Race
- Weight (kg)
- Height (cm)
- Body Mass Index (BMI kg/m^2)

Age (years) is the Baseline Age derived using the expression in section 6.5.1.

Age Category is this calculated value, Age (years), categorized into the groups:

- < 65 years
- $\geq$  65 years

Race is recorded in the eCRF by choosing all of the following classifications that apply:

- Asian
- Black/African-American
- White/Caucasian
- American Indian or Alaska Native
- Native Hawaiian or Other Pacific Islander
- Unknown
- Other

The subjects' choices will be summarized to show the number and percentage of subjects in the following categories for each of the starting dose groups and these two treatment groups combined:

- Asian Only
- Black/African-American Only

- White/Caucasian Only
- American Indian or Alaska Native Only
- Native Hawaiian or Other Pacific Islander Only
- More Than One Race
- Unknown
- Other

Only those categories with at least 1 subject will be displayed in the Baseline Demographic tables.

Subjects with more than 1 of the 5 categories, Asian, Black/African-American, White/Caucasian, American Indian or Alaska Native, Native Hawaiian or Other Pacific Islander selected on the eCRF Demography page are to be counted in the “Multiple” category.

Calculate Baseline BMI using the expression below where the values for weight and height values are baseline values.

$$\text{BMI (kg/m}^2\text{)} = [\text{Weight (kg)}] / [\text{height (m)}]^2.$$

Since height and weight are recorded in inches and pounds, respectively, note that

$$\text{Weight (kg)} = \text{Weight (lb)} / 2.2046$$

$$\text{Height (m)} = 0.0254 * \text{height (in)}.$$

Round weight and height to one decimal place before calculating BMI and round BMI to one decimal place.

Descriptive statistics of the following CKD characteristics will be presented in a table separate from the other characteristics:

- Age (years) at CKD Diagnosis
- CKD Primary Cause
- Baseline CKD Stage

Age at CKD Diagnosis is the CKD initial diagnosis age derived using the expression in section 6.5.1.

Other baseline characteristics include:

- Work Productivity and Activity Impairment Scores (See section 11.2 for scoring instructions.)

- Percent work time missed due to anemia associated with CKD
- Percent impairment while working due to anemia associated with CKD
- Percent overall work impairment due to anemia associated with CKD
- Percent activity impairment due to anemia associated with CKD
- FACIT-Fatigue Subscale Score (See section 11.4 for scoring instructions.)
- Number of hospitalizations
- Duration of hospitalization stay (days)
- The baseline evaluation for the following parameters reported by the central laboratory:
  - Hemoglobin (Hgb)
  - Estimated glomerular filtration rate (eGFR)
  - eGFR category: <30, 30 - 44, and >=45 ml/min/1.73m^2
  - Transferrin saturation (TSAT)
  - Ferritin
  - Phosphorus, i.e., serum phosphate
  - Intact parathyroid hormone (iPTH)
  - Intact Fibroblast growth factor 23 (iFGF23)
  - C-terminal Fibroblast growth factor 23 (cFGF23)
  - Spot urine protein-to-creatinine ratio

Descriptive statistics of the laboratory parameters will be displayed in conventional units.

#### **7.4. Medical History and Medical Conditions Present at Entry**

No table showing the number and percentage of subjects who had each medical history condition coded to MedDRA version 20.0 system order class (SOC) and preferred term (PT) or by subject data listings will be presented. The missing start and stop dates will be imputed as described in section 6.6.2 and included in the ADaM dataset.

#### **7.5. Prior and Concomitant Medications and Non-Drug Therapies**

All prescription and over-the-counter medications and non-drug therapies used by subjects at Visit 1A (Screening) and thereafter through the last study visit will be recorded in the eCRF.

WHO-DD version 01Jun2017 B2 format will be used to code the medications. Non-drug therapies will not be coded.

Prior medications and therapies are defined as any that were started and stopped prior to the date the subject used the first dose of the study drug. Concomitant medications and therapies are defined as any that were started or were ongoing on or after the study drug first dose date up to and including the last study visit date.

No by subject data listings or tables showing the prior or concomitant medications recorded in the eCRF will be presented.

Incomplete start and/or stop dates for the medications and therapies recorded in the eCRF will be imputed as follows:

- If either the start of medication or other therapy date is completely missing, or the month and/or year of the start date is missing, the start date will be set to the first dose date.
- If only the day is missing, the day will be set to the first day of the month except if the start month is the same as the first dose month. If the latter is true, the start day will be set to the first dose day.
- If stop date is completely missing, it will be assumed that use of the medication is ongoing, and it will be classified as a concomitant medication with a missing stop date.
- If stop date is partially missing, then impute as the latest possible date given date parts that are not missing. (I.e., if only day is missing then impute as last day of the given month and if month and day are missing then impute as Dec. 31st of the given year.)

## 8. EFFICACY

### 8.1. General Considerations

Efficacy analyses will be based on the PP Analysis Set data for the 24-Week and Final analyses (mPP Analysis Set for 24-Week analysis snapshot). Additionally, efficacy of the study drug in the FAS subgroup of subject who received rescue therapy under the conditions specified in section 9.2.2 of protocol will be assessed.

Table 3 lists the efficacy endpoints of special focus for the 24-Week Analysis snapshot and the 24-Week and Final Analyses showing the analysis method and analysis set to be used in assessing them. See section 8.2 for any special conditions to be explored for implementation of the analysis method or alternatives that will necessitate implementation of an alternative method.

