2. SYNOPSIS

Name of Sponsor/Company: Keryx Biopharmaceuticals, Inc.	
Name of Investigational Product: KRX-0502 (ferric citrate)	
Name of Active Ingredient: Ferric citrate	
Title of Study: A Phase 4 study of KRX-0502 (ferric citrate) dose regimens in subjects with non-dialysis dependent chronic kidney disease and iron deficiency anemia: the COMPASS Trial	
Study center(s): Multicenter; approximately 30 sites in the United States	
Studied period (years): Estimated date first subject enrolled: 3 rd Quarter 2017 Estimated date last subject completed: 2 nd Quarter 2019	Phase of development: 4
Objectives: The objectives of this study are to assess the long-term efficacy and safety of different dose regimens of KRX-0502 in the treatment of iron deficiency anemia (IDA) in adult subjects with non-dialysis dependent chronic kidney disease (CKD).	
Methodology: This is a 48-week, Phase 4, randomized, open-label, multicenter clinical study comprised of 2 periods: a 24-week Dose Titration Period, followed by a 24-week Dose Maintenance Period. The study will consist of 12 scheduled clinic visits over a period of 48 weeks and additional visits as needed. Approximately 200 eligible subjects with non-dialysis dependent CKD and IDA will be randomized in the study into 1 of 2 active treatment groups: 
 • Group 1: KRX-0502 1 tablet thrice daily (TID; total of 3 tablets/day) with meals • Group 2: KRX-0502 2 tablets twice daily (BID; total of 4 tablets/day) with the largest 2 daily meals At Week 12, those subjects with a hemoglobin (Hgb) increase of ≥ 0.5 g/dL from Baseline and an Hgb ≥ 10 g/dL will maintain the same dose, otherwise their dose will be increased as follows: 
 • Group 1: KRX-0502 2 tablets TID (total of 6 tablets/day) with meals • Group 2: KRX-0502 3 tablets BID (total of 6 tablets/day) with the largest 2 daily meals 	
Number of subjects (planned): Two hundred (200) subjects are planned to be randomized	
Diagnosis and main criteria for inclusion: Inclusion criteria Subjects meeting all of the following inclusion criteria will be randomized in this study: 
 1. Age ≥ 18 years 	

2. Men and women. Women of childbearing potential must have a negative serum pregnancy test at Screening
3. Estimated glomerular filtration rate ≥ 20 mL/min and < 60 mL/min at Screening
4. Hgb ≥ 8.5 g/dL and ≤ 11.5 g/dL at Screening

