9.2.2. ESA Rescue Therapy

ESA use is not permitted during the study. The exception is a scenario in which all of the following conditions for ESA rescue therapy are met:

1. A subject has had 2 consecutive Hgb values of <8.0 g/dL more than 3 days apart.
2. The Investigator decides to treat the subject with ESA as per standard of care.
3. The Investigator deems it appropriate for the subject to continue in the study.
4. The subject continues in the study on study drug.

Any subject who is to receive or has received ESA therapy regardless of whether its use constitutes permitted ESA rescue therapy or not should be discussed with the Medical Monitor as soon as possible to decide whether the subject may remain in the study.

Subjects who received ESA during the study and who remain in the study will be excluded from the PP analysis set. Subgroup analyses will be conducted for these subjects.

Subjects who have had 2 consecutive Hgb values of <8.0 g/dL more than 3 days apart but do not meet the other criteria of ESA rescue therapy should complete the ET visit and discontinue from the study.

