#### **8.4. Subgroup Analyses**

For the 24-Week analysis, the change from baseline at Week 24 in Hgb, TSAT, ferritin, and phosphorus will be assessed for subjects who received 'Permitted' ESA therapy during the Dose Titration Period. For the Final analysis, the change from baseline at Week 24 and at Week 48 in Hgb, TSAT, ferritin, and phosphorus will be assessed for subjects who received 'Permitted' ESA therapy during the study.

Data in the Full Analysis Set for this subgroup of subjects will be used for the analyses. If at least 30 subjects are in the subgroup descriptive statistics and the two-sided 95% confidence intervals for the mean change from Baseline will be obtained as described in section 8.2 for the change from Baseline Hgb. If this subgroup includes at least 3 subjects but less than 30 subjects, only descriptive statistics will be presented for each of the starting dose treatment groups. For the Final analysis only, if less than 3 subjects are in the subgroup by subject listings of disposition, demographics, and laboratory tests (hematology, chemistry, urine chemistry, and miscellaneous) will be provided instead of summary tables.

It is expected that after the planned dose titration at Week 12 there will be about 35 subjects in each of the 4 dosing sequence groups,

(Starting Dose Group Daily Dose (pills/day) – Week 12 Titrated Daily Dose (pills/day), i.e.:

- 3 pills/day – 3 pills/day,
- 3 pills/day – 6 pills/day,

- 4 pills/day – 4 pills/day and
- 4 pills/day – 6 pills/day.

For the Final analysis, additional subgroup analyses will be conducted for change from baseline in Hgb, TSAT, ferritin, and phosphorus in these dosing sequence groups. The 95% confidence interval for the mean change from baseline for each dosing sequence will be obtained by using dosing sequence rather than starting dose treatment group in the MMRM model described in section 8.2. Each subject's dosing sequence group will be based on the actual dose prescribed at baseline and the Week 12 dose titration assignment. If the subgroups include at least 3 subjects but less than 30 subjects, the MMRM analysis will not be performed and only descriptive statistics will be presented. For the Final analysis only, if there are less than 3 subjects in any subgroup, only by subject listings will be provided instead of tables.

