## 9.6. Summary of Changes from Protocol-Specified Analyses

- The protocol states that “All subjects who are randomized and take at least 1 dose of study medication will be included in the Safety Analysis Set.” However, the Safety Analysis Set is being defined as the set of all subjects who receive at least one dose of study medication, to allow for the highly unlikely possibility that some subject (s) may receive a dose of medication prior to being randomized.
- The protocol did not discuss the potential for an ad hoc analysis. The analysis is acknowledged in this SAP and more details will be added to an amended SAP if an analysis is performed.
- The protocol did not discuss the modified Per Protocol Analysis Set. This analysis set is described in section 6.3.6 and is used for the 24-Week analysis snapshot only.
- The SAP describes analyses for the following secondary efficacy endpoints which were not included in the protocol:
  - Time from randomization to first hemoglobin increase of  $\geq$  0.5 g/dL from Baseline.
  - Change from the baseline value for each of the following:
    - eGFR
    - serum bicarbonate
    - intact parathyroid hormone
    - C-terminal fibroblast growth factor 23
    - intact fibroblast growth factor
  - Inclusion of box and scatter plots over time of the observed value and the change from Baseline for each of the iron parameter efficacy variables, TSAT and ferritin to explore the question of their stability over time on treatment.
- The protocol specified analyses of vital signs is not included in the SAP, since no related safety concerns are anticipated.

- The protocol states that all efficacy analyses will be performed based on both the FAS and the PP/mPP analysis sets, however only the PP/mPP analyses sets will be considered. Subjects are excluded from the PP/mPP analysis sets due to confounders of efficacy and thus the FAS is not appropriate for efficacy analyses. The FAS will be used for the efficacy analysis for the 'Permitted' ESA Rescue Therapy subgroup.
- The protocol did not include the baseline by visit interaction term in the efficacy model. This interaction term is included in the SAP and will be included in the model.
- Missing endpoint observations will not be imputed using a multiple imputation (MI) linear regression approach for use in an additional sensitivity analysis as specified in the protocol sections 15.7.2 and 15.10.3.

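### The permitted-ESA subgroup analysis is labelled as study-drug efficacy but does not separate values before and after the first ESA dose

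*SAP*

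**What the plan says.** Protocol 9.2.2 permits ESA rescue only under set conditions. The first is "A subject has had 2 consecutive Hgb values of <8.0 g/dL more than 3 days apart" and the last is "The subject continues in the study on study drug". It removes ESA users from the PP set and asks for subgroup analyses of them, without calling these a measure of study-drug efficacy.

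That label comes from SAP 8.1, which plans to assess "efficacy of the study drug in the FAS subgroup of subject who received rescue therapy". SAP 7.3 and 9.6 also refer to efficacy analysis of this subgroup.

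SAP 8.4 defines the analysis. In the 24-Week analysis, the change at Week 24 "will be assessed for subjects who received 'Permitted' ESA therapy during the Dose Titration Period". In the Final analysis, the changes at Weeks 24 and 48 "will be assessed for subjects who received 'Permitted' ESA therapy during the study". The variables are Hgb, TSAT, ferritin and phosphorus. With 30 or more subjects there are 95% confidence intervals from the SAP 8.2 model; with 3 to 29 there are descriptive statistics only. Table 3 gives the method as MMRM.

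SAP 6.3.5 and 6.3.6 exclude any subject with ESA use, permitted or not, from the PP and mPP sets. SAP 9.6 gives the reason: "Subjects are excluded from the PP/mPP analysis sets due to confounders of efficacy and thus the FAS is not appropriate for efficacy analyses". It then makes an exception and uses the FAS for the permitted-ESA subgroup.

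**The concern.** An analysis described as efficacy of KRX-0502 should rest on values that KRX-0502 could have produced. Here a second anaemia treatment has been added, and it was added because Hgb was low. A later value therefore carries three things at once: continued KRX-0502, the ESA, and the tendency of a value selected for being low to move back up. The SAP recognises ESA as a confounder when it builds the PP and mPP sets, but gives no rule for handling it where every subject has received it.

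The stake is limited but real. This is the only planned efficacy output that contains rescued subjects. A reader could not undo the mixing from the planned outputs: SAP 7.5 plans no table or listing of concomitant medications, and the asterisk in listings (SAP 6.2) marks the subject, not the date ESA began.

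**Working it through.** **1. The plan's own figures.** Half-width = 1.96 × SD/√n = 1.96 × 0.9/√140 = 0.149 g/dL, and 140/0.70 = 200 randomised. Both reproduce and neither is in dispute. They are used below only for scale.

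**2. What each planned value represents.**

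| Analysis and visit | Who is included | State of the value |
|---|---|---|
| 24-Week analysis, Week 24 | Permitted ESA in the Dose Titration Period | After ESA start, apart from edge cases of timing |
| Final analysis, Week 24 | Permitted ESA at any time in the study | After ESA for those rescued by then; before ESA for those rescued later |
| Final analysis, Week 48 | Permitted ESA at any time in the study | After ESA start, apart from edge cases of timing |

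No other section supplies a rule. SAP 6.6.1 deals with missing values only. SAP 6.5.4 takes the latest assessment in a visit window, whatever the ESA status.

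For the Final analysis at Week 24, let f be the share of the subgroup first rescued after that visit. The observed mean is f × m(before) + (1 − f) × m(after). The first component comes from subjects chosen because of an event still to come, the second from subjects on two treatments. The documents give no value for f or for either mean.

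**3. Illustration of scale (not an estimate).** Protocol entry requires "Hgb ≥ 8.5 g/dL and ≤ 11.5 g/dL at Screening" and rescue requires values below 8.0. Let b be entry Hgb, taken as Baseline, and r the rise in Hgb after ESA begins. The documents give no figure for r, so it is assumed. Reported change = 8.0 + r − b, in g/dL:

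| b | r = 0 (at trigger) | r = 1 | r = 2 | r = 3 |
|---|---|---|---|---|
| 8.5 | −0.5 | +0.5 | +1.5 | +2.5 |
| 10.0 | −2.0 | −1.0 | 0.0 | +1.0 |
| 11.5 | −3.5 | −2.5 | −1.5 | −0.5 |

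The trigger is below 8.0, so the r = 0 column is an upper bound. The sign turns positive only if r exceeds b − 8.0, that is 0.5, 2.0 or 3.5 for the three rows. Two approximations apply. SAP 6.4 takes Baseline as the last value before the first dose, not the Screening value. The original protocol's trigger was 8.5 (Protocol Appendix C; SAP 7.1 still carries that threshold for subjects not qualifying for rescue), which would add 0.5 to each cell for a subject rescued under it.

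**4. When an interval would appear.** The MMRM interval needs 30 rescued subjects, and 30/200 = 15% of those randomised. If the planning SD of 0.9 held in this subgroup (an assumption), the half-width at n = 30 would be 1.96 × 0.9/√30 = 0.32 g/dL. That interval would describe sampling error only; it would not reflect the mixture in steps 2 and 3. With 3 to 29 subjects no interval is shown, but the means mix the same effects.

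**The case against.** The case for leaving the plan alone has several sound parts.

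- The subgroup is not disguised. Table 3 and SAP 8.4 name it as permitted-ESA subjects, and listings flag them.
- The main results are clean, because any ESA use removes a subject from PP and mPP.
- Protocol 9.2.2 asked for subgroup analyses of these subjects, and SAP 9.6 states the FAS exception openly. Keeping confounded subjects out of the main analysis and describing them separately is coherent.
- Below 30 subjects the output is already descriptive.
- Rescued subjects' laboratory values also enter the Safety Analysis Set summaries, shift tables and listings in SAP 9.4, where Hgb below 8.0 is a flagged category in Table 4.

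All of this stands. It narrows the point to what the subgroup result is said to mean and how its values are pooled. It does not answer that point: a correctly named subgroup can still carry a conclusion that its values cannot support, and none of the planned medication or laboratory displays supplies the ESA start date.

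A reader might go further and infer that the ESA effect is being reported as a KRX-0502 result in subjects in whom KRX-0502 had failed. The documents do not support that. Values after rescue are a mixture, not the ESA effect alone, and some Week 24 values in the Final analysis precede ESA altogether. Failure is an inference: the trigger is an Hgb level, and the dose may have been reduced or interrupted under Protocol 7.5.2. The lack-of-efficacy entry in Protocol 8.3.1 does point to the rescue section, but as a reason for stopping a drug that rescued subjects continue.

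**Conclusion.** The point holds in a limited form. As written, SAP 8.1 promises study-drug efficacy in permitted-ESA subjects, while SAP 8.4 and Table 3 deliver a change from Baseline that mixes KRX-0502, ESA and regression from a low trigger. In the Final analysis at Week 24 they also pool subjects before and after rescue. The result cannot be read as an effect of KRX-0502.

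The size of the distortion cannot be computed, since neither the number of rescued subjects nor the Hgb rise after ESA is given. The illustration shows only that the sign of the reported change depends on that unstated rise. It would be wrong to conclude that the plan will show failures as successes: with an entry Hgb of 11.5, the change stays negative even at an assumed rise of 3 g/dL. It would also be wrong to extend the point to the primary analysis, which excludes these subjects.

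**What to change.** - **SAP 8.1:** replace the study-drug efficacy label for this subgroup with a description, for example *course of Hgb, TSAT, ferritin and phosphate in subjects given permitted ESA rescue*. In SAP 9.6 drop the term efficacy analysis for this subgroup, and align SAP 7.3.
- **SAP 8.4 and Table 3:** report values before and after the first ESA dose separately and descriptively, by starting dose. Present no MMRM interval as a study-drug effect.
- **Caveat to print with the pre-ESA values:** the last Hgb before ESA is low by selection, because two low values are the condition for entering the subgroup. It is not an unbiased on-drug estimate.
- **Final analysis, Week 24:** split the subgroup by whether ESA had started.
- **Listing:** show the ESA start date for each of these subjects.
- **Incomplete ESA dates:** write a specific rule. SAP 7.5 sets a start date with missing month or year to the first dose date, which would leave no on-treatment value before ESA, and SAP 6.6.2 limits imputed dates to classifying a medication as concomitant. One option is to use the second qualifying Hgb value as the earliest possible start of permitted rescue, and to report values that cannot be placed as undetermined.

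The cost is modest: wording, one flag built from medication dates already collected, one listing and one date rule. The main drawback is smaller cells in a subgroup that may already be small.
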